4.2 VTX-801 Dose Escalation

Adult male and female WD patients receiving SoC therapy with either zinc salt, a copper chelator (D-penicillamine or trientine) or the association thereof and who meet all eligibility criteria will be sequentially enrolled and treated with escalating doses of VTX-801 in up to 3 consecutive cohorts of approximately 4 patients each; each patient will receive a single VTX-801 infusion, starting with a potentially therapeutic dose (Section 7.2). The best efforts will be made to enroll at least 1 patient of each gender in each cohort of 4.

Note for patients receiving chelators or dual chelator and zinc therapy, a chelator wash-out period will be required around each radiocopper injection (starting 3 days before radiocopper injection and continuing until the end of the radiocopper investigations – refer

[figure not shown]
Protocol VTX-801_CLN_001	Investigational Product: VTX-801
	Version: 9 dated 07 AUG 2023
	Author: Aixial Group CRO

to Sections 8.2.6.1 and 8.2.6.2) planned during the week preceding the VTX-801 administration and at Weeks 12 and 36 from VTX-801 administration. The objective of the wash-out period is to prevent any possible interference of chelators with 24-hour urinary copper and radiocopper assessments (no wash-out is required for patients on any zinc-only treatment). Importantly, such a short wash-out period is not considered to put patients at risk, since accumulation of copper is a slow process.

Dose escalation will proceed according to the following enrollment scheme (refer to the Enrollment Decision Tree in [Figure 2](#) and the Stopping Rules in Section 6.3):

- \geq 6-week intervals will be maintained between the VTX-801 infusion of the first 2 patients of each cohort
- if VTX-801 is well tolerated in both patients, as per the pre-defined Stopping Rules outlined in Section 6.3, then \geq 12-week data (W12) from the first 2 patients of each cohort will be reviewed by the Sponsor and the DMC:
 - if first 2 patients are VTX-801 Responders at W12 (see Section 4.5), the remaining 2 patients of the concerned cohort may be enrolled; the decision of dose escalation will be based on the review of all available safety data of 3 to 4 patients at 12 weeks by the DMC. If well tolerated according to DMC, dose escalation may proceed after Sponsor agreement.

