10.2 Visits 2-5: Baseline and Pre-VTX-801 Period

Duration: 4 study visits within a period of 7 days:

- **Visit 2;** Baseline: 1-day outpatient visit, which will also include the initiation of Sirolimus treatment [REDACTED].
- Flexibility of up to 7 additional days for VTX-801 administration is allowed if needed in order to comply with radiocopper production constraints or to accommodate the sites and/or patients. As a consequence, initiation of the

Protocol VTX-801_CLN_001	Investigational Product: VTX-801
	Version: 9 dated 07 AUG 2023
	Author: Aixial Group CRO

Sirolimus treatment [REDACTED] will then need to be shifted accordingly (start 7 days prior to VTX-801 administration).

- No visits for 3 days.
- **Visits 3-4-5:** a 3-day in- or outpatient visit period during [REDACTED].

Refer to [Table 2](#) Summary of Schedule of Events: Baseline to Week 12

(Note permitted visit windows are allowed for some assessments; refer to [Table 2](#) and its footnotes)

Visit 2	Day -7	Baseline	Outpatient visit	Cross-reference
Vital signs				Section 8.1.4
Physical examination				Section 8.1.3
Alcohol consumption				Section 7.7
Serum pregnancy test (for WOCBP only)				Section 8.1.12
Central Laboratory: blood/urine biochemistry; hematology; coagulation				Section 8.1.11
Central Laboratory: Liver biochemistry panel				Section 8.1.11
Local Laboratory: Liver biochemistry panel				Section 8.1.12
Calculation of MELD, APRI, FIB4 by CRO				Table 11
Ceruloplasmin (enzymatic assay and nephelometry), CuEXC, total Cu, REC, RAC, ANCC, CRP				Section 8.1.13
ELISA and IFN-gamma ELISpot				Section 8.2.4
Ophthalmology: slit lamp examination. It can be performed from Baseline V2 to the day before radiocopper administration as long as results are available before the day of radiocopper administration.				Section 8.1.6

Protocol VTX-801_CLN_001	Investigational Product: VTX-801 Version: 9 dated 07 AUG 2023 Author: Aixial Group CRO
--------------------------	--

For Visits 3-4-5, patients **from expansion cohort (only)** will be hospitalized, stay at a unit with clinical support or other location approved by the [REDACTED]

Refer to Table 2 Summary of Schedule of Events: Baseline to Week 12				
Visit 3	Day -3	Pre VTX-801	In or Out-patient visit	Cross-reference
Vital signs				Section 8.1.4

Protocol VTX-801_CLN_001	Investigational Product: VTX-801
	Version: 9 dated 07 AUG 2023
	Author: Aixial Group CRO

Physical examination	Section 8.1.3
Sirolimus	Section 7.5

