Sirolimus level test: sampling for blood trough concentration 4-5 days after starting treatment with Sirolimus	Section 7.5
[REDACTED]	[REDACTED]
24-hour urinary copper (to end prior to radiocopper administration)	Section 8.1.13
[REDACTED]	[REDACTED]
Radiocopper administration (around 9 am)	Section 7.4
[REDACTED]	[REDACTED]
[REDACTED]	[REDACTED]
[REDACTED]	[REDACTED]
Adverse events	Section 9.2
Prior medications	Section 8.1.2

Refer to Table 2 Summary of Schedule of Events: Baseline to Week 12				
Visit 4	Day -2	Pre VTX-801	In or Out-patient visit	Cross-reference
Vital signs				Section 8.1.4
Sirolimus				Section 7.5
[REDACTED]				[REDACTED]

Protocol VTX-801_CLN_001	Investigational Product: VTX-801
	Version: 9 dated 07 AUG 2023
	Author: Aixial Group CRO

[REDACTED]	[REDACTED]
Adverse events	Section 9.2
Concomitant medications	Section 8.1.2

Refer to Table 2 Summary of Schedule of Events: Baseline to Week 12				
Visit 5	Day -1	Pre VTX-801	In or Out-patient visit	Cross-reference
Vital signs				Section 8.1.4
Weight				Section 8.1.3
Sirolimus				Section 7.5
[REDACTED]				[REDACTED]
Vector shedding: blood, urine, saliva, feces - mandatory				Section 8.2.3
Vector shedding: At Day -1 baseline starting after last radiocopper sampling				Section 8.2.3

Protocol VTX-801_CLN_001	Investigational Product: VTX-801
	Version: 9 dated 07 AUG 2023
	Author: Aixial Group CRO

and within 24 hours before VTX-801, taking into account +7D window for administration. These assessments are to be performed either at V5 or V6.	
Adverse events	Section 9.2
Prior medications	Section 8.1.2

10.3 Visit 6: Day 1, Week 1

This is the first day of the inpatient period related to VTX-801 administration. The patient will then be hospitalized overnight and will be discharged on the following day.

If the patient's medical status post-VTX-801 administration necessitates a prolonged hospitalization, please refer to Section [9.3](#) Serious Adverse Events.

Flexibility of up to 7 additional days for VTX-801 administration is allowed if needed in order to comply with radiocopper production constraints or to accommodate the sites and/or patients.

Home nurse collected samples for liver biochemistry panel may be sent to the Central Laboratory instead of to the Local laboratory.

Refer to Table 2 Summary of Schedule of Events: Baseline to Week 12				
Visit 6	Day 1 + 7 days	VTX-801	Inpatient visit	Cross-reference
Special instructions:				Section 7.2

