10.5.7 Visits 26-29 (Week 12)

Only for the expansion cohort: the patient is to be hospitalized, stay at a unit with clinical support or other location approved by the Sponsor [REDACTED]

Refer to Section [10.2](#), Visit 2 for the wash-out instructions for patients on copper chelators or dual chelator and zinc therapy:

Refer to Section [7.6.3](#), for expansion cohort only, [REDACTED]

The 2 samples of Week 12 for “Liver biochemistry panel” will occur at site as much as possible. For example, at Visit 26 collecting the first sample is mandatory, with the second sample collected at Visit 28 or Visit 29.

If the second sample cannot occur at site, it should be collected at the home nurse visit planned after end of hospitalization within Week 12 (Visit 30).

Refer to Table 2 Summary of Schedule of Events: Baseline to Week 12				
Visit 26	Week 12 ± 5 days	Follow-up	In or Out-patient visit	Cross-reference
Vital signs				Section 8.1.4

Protocol VTX-801_CLN_001	Investigational Product: VTX-801
	Version: 9 dated 07 AUG 2023
	Author: Aixial Group CRO

Physical examination	Section 8.1.3
Alcohol consumption	Section 7.7
Urine pregnancy test (for WOCBP only)	Section 8.1.12
Central Laboratory: Blood/urine biochemistry; hematology; coagulation	Section 8.1.11
Central Laboratory: Liver biochemistry panel	Section 8.1.11
Local Laboratory: Liver biochemistry panel (twice per week)	Section 8.1.12
Calculation of MELD, APRI, FIB4 by CRO	Section 8.1.14 Table 11
Ceruloplasmin (enzymatic assay and nephelometry), total Cu, REC, RAC, CuEXC, ANCC	Section 8.1.13
24-hour urinary copper (to end prior to radiocopper administration)	Section 8.1.13
For patients on copper chelator: 
 Patients are to be informed to start the wash-out period without copper-chelator treatment 3 days before radiocopper injection and until the end of the radiocopper investigations. The 24-hour urine copper sample will start 48 hours after initiation of the chelator wash-out period and will end prior to radiocopper administration 	
Vector shedding: blood, urine, saliva, feces Note: at all visits until end of year 1, as applicable but only at this visit during this period of 4 consecutive visits (V26 to V29).	Section 8.2.3
ELISA and IFN-gamma ELISpot	Section 8.2.4
ECG	Section 8.1.5

Protocol VTX-801_CLN_001	Investigational Product: VTX-801
	Version: 9 dated 07 AUG 2023
	Author: Aixial Group CRO

UWDRS, M.I.N.I., SDMT and Stroop Test	Section 8.1.7
[REDACTED]	[REDACTED]

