11.1 Sample Size Considerations

Sample size has not been determined based upon statistical calculations. The sample size of up to approximately 16 patients, with approximately 4 patients per cohort, was chosen based on scientific judgment to have sufficient replication to meet the study objectives.

The best efforts will be made to enroll at least 1 patient of each gender in each cohort of 4.

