11.4 Statistical Methodology

All statistical analyses will be descriptive, there will be no hypothesis testing. Continuous variables will be summarized using descriptive statistics (n, mean, standard deviation, median, minimum, and maximum). Categorical variables will be summarized showing the number and percentage (n, %) of patients within each classification.

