5.3 Data Derivations

Baseline and Change from Baseline

Baseline and change from baseline will be calculated for all assessments, including additional assessments (if applicable), as follows:

- Baseline value is defined as the last available value prior VTX-801 dosing, if not defined otherwise in the study protocol. Assessments that occurred on the same day as VTX-801 dosing, when time of assessment is not available, will be assumed to be prior to VTX-801 dosing (unless the assessment is planned after VTX-801 dosing in the study protocol).
- Change from baseline will be calculated for any post-baseline data as the difference between the post-baseline assessment value and the baseline value.

Study Day

Study day will be calculated as (assessment/sample date – date of first study treatment dose) for pre-baseline assessments and [(assessment/sample date – date of first study treatment dose) + 1] for post-baseline assessments, i.e., there will be no study day 0 and study day 1 will correspond to the first study treatment dose.

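### In chelator-treated patients, serum copper change from baseline compares an on-chelator Day -7 sample with washed-out samples at Week 12 and, if radiocopper is given, at Week 36

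*Protocol*

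**What the plan says.** - **Wash-out.** Protocol 4.2 requires a chelator wash-out around each radiocopper injection, "starting 3 days before radiocopper injection and continuing until the end of the radiocopper investigations". Its stated purpose covers 24-hour urinary copper and radiocopper; serum copper is not mentioned. Patients on zinc alone have no wash-out (4.2, 7.1.1).
- **Baseline serum.** Protocol 10.2 lists this panel at Visit 2, Day -7: "Ceruloplasmin (enzymatic assay and nephelometry), CuEXC, total Cu, REC, RAC, ANCC, CRP". Between Visits 2 and 3 the schedule reads "No visits for 3 days".
- **Baseline radiocopper and urine.** Visit 3, Day -3, carries "Radiocopper administration (around 9 am") and a 24-hour urine collection that must finish before the injection.
- **Week 12.** Protocol 10.5.7 lists the serum panel and the urine at Visit 26 and instructs chelator patients to "start the wash-out period without copper-chelator treatment 3 days before radiocopper injection".
- **Week 36.** Protocol 10.5.13 has the same arrangement at Visit 39, but radiocopper is given only if applicable; otherwise the patient attends Visit 39 alone.
- **Analysis.** Protocol 11.4.5 plans absolute values, change and percent change for these markers. SAP 5.3 applies change from baseline to all assessments and says "Baseline value is defined as the last available value prior VTX-801 dosing". SAP 7.8 lists the pharmacodynamic endpoints, and SAP section 9 limits their analysis to descriptive statistics.

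**The concern.** Free serum copper (CuEXC, ANCC), REC, RAC and total serum copper are secondary endpoints (Protocol 3.2.2). If the baseline sample is taken on a chelator and the follow-up sample three days off it, the difference contains any effect of VTX-801 plus any effect of stopping the chelator. There is no control arm, and SAP section 9 reports two patients in each of two cohorts, so nothing in the data separates the two. Patients on zinc alone carry no such component, so a cohort that mixes background therapies also mixes two kinds of change. The protocol deals with chelator interference for urine, which is collected off chelator at baseline, Week 12 and Week 36, but does not do the same for serum. Neither document flags chelator state at the serum draw or allows for it in the analysis.

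**Working it through.** There is no power or precision figure to reproduce: "Sample size has not been determined based upon statistical calculations", and "All statistical analyses will be descriptive, there will be no hypothesis testing". The check is of timing, then of whether redaction could hide a second baseline draw.

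**1. Timeline (planned days).** Wash-out start = injection day minus 3 days.
- Baseline: Day -3 minus 3 = Day -6. The serum draw on Day -7 comes one day earlier, so it is on chelator.
- Urine: Protocol 10.5.7 starts collection 48 hours into the wash-out and runs it for 24 hours. Applied to baseline, that is Day -4 to Day -3, inside the wash-out.

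| Time point | Serum copper panel | 24-hour urine |
|---|---|---|
| Baseline | V2, Day -7: on chelator | V3: off chelator |
| Week 4 | V10, no wash-out stated: on chelator | not listed |
| Week 12 | V26: off chelator | V26: off chelator |
| Week 36, radiocopper given, still on a chelator | V39: off chelator | V39: off chelator |

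Patients withdrawn from background therapy at Week 14 would be off chelator for about 22 weeks by Week 36 (36 - 14), also unlike baseline. SAP 4.1 states that withdrawal did not occur, so for the dosed patients the wash-out is the relevant case.

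**2. Could a copper draw be hidden between Day -7 and dosing?** Undisclosed volume = column total minus visible rows, from Tables 18 and 19.
- V2: 2 + 16 + 5 + 5 + 7 + 12 + 4 + 50 = 101 mL, total 101, undisclosed 0.
- V3, V4, V5, V6: 33 - 3 = 30; 20 - 0 = 20; 21 - 1 = 20; 24 - 4 = 20 mL.
- V26, V27, V28, V29: 130 - 100 = 30; 20 - 0 = 20; 20 - 0 = 20; 26 - 6 = 20 mL.
- V39, V40, V41, V42: 76 - 46 = 30; 20 - 0 = 20; 20 - 0 = 20; 26 - 6 = 20 mL.

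The pattern 30/20/20/20 repeats around each radiocopper occasion. At V26 and V39 the two copper rows (7 + 12 = 19 mL) are itemised in addition to the 30 mL, so the undisclosed blood is not the copper panel. Those rows are empty at V3 to V6. The pattern also supports V26 as the injection visit: no radiocopper line is visible there, but the urine listed at that visit must end before the injection. The tables reconcile overall: 86 + 686 + 316 + 400 = 1,488 mL, as stated in Protocol 8.3.

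**3. Size.** The documents give none. As an assumption, let a three-day chelator stop shift a serum marker by s percent of baseline, with s from 0 to 30 in either direction. One patient's percent change is then off by s points, and a cohort mean by (share of cohort on a chelator) x s.
- Cohort of 2, one on a chelator: 1/2 x 30 = at most 15 points. Both on a chelator: at most 30.
- Cohort of 4, as planned: one on a chelator, 1/4 x 30 = at most 7.5 points; two, at most 15; all four, at most 30.
- At s = 0 there is no distortion.

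**The case against.** The strongest reply is that little current output depends on this. Under SAP 1.0 the Pharmacodynamics Set is not used, the serum copper endpoints are to be listed, and within SAP section 7 only the ECG paragraph asks explicitly for change from baseline. This largely stands and lowers the impact. It does not remove the point. SAP 5.3 still defines change for all assessments, section 9 still speaks of descriptive statistics, and a listing without chelator state invites the same misreading.

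Some of the evidence is also out of sight. Protocol 10.2 refers to permitted windows in the Table 2 footnotes, and these, like the Visit 2 wash-out instructions, are not visible. A footnote allowing a later serum draw cannot be excluded. Against that, Table 18 itemises no such draw, and the text gives a baseline window for the slit lamp and the questionnaires but none for serum copper.

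A reader might also infer more than the documents support:
- **A material shift in one direction in every chelator patient.** No size or direction is given, and two different chelators are allowed.
- **A comparison with the CuEXC limit of 0.40 in Protocol 9.7.** That limit is a criterion for an absolute value, not for a change.
- **A distorted Responder status or escalation decision.** The Protocol Summary bases response on radiocopper assessments, and the definition in 4.5 is redacted.
- **No off-chelator serum reference for the dosed patients.** Both screening visits list CuEXC, REC and total copper beside a 24-hour urine that Table 11 requires after a two-day wash-out. Whether the blood was drawn in that window is not stated.
- **A washed-out Week 36 sample in all chelator patients.** That wash-out is tied to an injection that is conditional.

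**Conclusion.** The mismatch holds on the visible text for patients on a chelator, alone or with zinc. The baseline serum copper panel precedes the wash-out by about one day. The Week 12 panel follows it, as does the Week 36 panel where radiocopper is given and the patient is still on a chelator. Change from Day -7 to those visits therefore cannot be read as an effect of VTX-801 alone.

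The confounding is structural and its size is unknown; it may be zero. The conclusion assumes that the planned visit days were kept and that no unseen footnote moves the draw. The number of affected patients among the four dosed is not stated and could be none. Urinary copper and zinc-only patients are not affected. Because the endpoints are mainly listed, this is worth correcting at low cost but does not undermine the primary safety analysis.

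**What to change.** **In SAP 5.3 and 7.8:**
- Add chelator state to every serum copper listing row: on or off and, where recorded, time since the last chelator dose. WD medications are already listed under SAP 7.6, so the state may be recoverable if interruptions were dated.
- Do not report or interpret change from the Day -7 value as a VTX-801 effect for samples taken in wash-out.
- Compare only samples in the same recorded state: Day -7 with Week 4, and Week 12 with Week 36 only where both were washed out.
- Apply the same flag at Weeks 24 and 52 and at later visits with a 72-hour chelator-free urine collection, since the protocol does not say when within that period serum is drawn.
- Check whether a screening sample (CuEXC, REC, total copper) was drawn off chelator and can serve as a matched reference.
- Reconcile SAP 5.3, 7.8 and section 9 on whether change in these endpoints is to be produced.

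**If the protocol is reused:** draw the baseline serum panel, about 19 mL, at Visit 3 before radiocopper, where it matches the urine. Sirolimus starts at Visit 2, so this sample would be taken after immunosuppression has begun, which should be weighed.

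**Cost:** one listing column and one derivation rule. For the dosed patients there may be no matched baseline for ANCC and RAC, which are not listed at screening.

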10.5.8 Visits 30 and 31 (Weeks 12 and 13 ± 3 days)

Refer to Table 3 Summary of Schedule of Events: Weeks 13 to 52 (End of Year 1) Note: Visit 30 will not occur (including recording vital signs) if the liver biochemistry sample is collected at either Visit 28 or Visit 29 at site				
Visits 30-31	Weeks 12,13 ± 3 days	Follow-up	Home nurse visits	Cross-reference
Vital signs				Section 8.1.4
Local Laboratory: Liver biochemistry panel (only if not done at either Visit 28 or 29)				Section 8.1.12
Sirolimus administration [REDACTED]				Section 7.5
[REDACTED]				[REDACTED]
Adverse events				Section 9.2
Concomitant medications				Section 8.1.2

10.5.9 Visit 32 (Week 14 + 2 days)

Refer to Table 3 Summary of Schedule of Events: Weeks 13 to 52 (End of Year 1) Note: Time window at W14 may be increased beyond 2 days to accommodate the DMC review process.				
Visit 32	Week 14 + 2 days	Follow-up	Phone call	Cross-reference
Vital signs (only if visit occurs on site)				Section 8.1.4
Investigator informs the patient about his/her "Responder/Insufficient Responder" status and associated consequences: • withdrawal or continuation of the WD SoC therapy				Section 4.5 / Section 4.6

Protocol VTX-801_CLN_001	Investigational Product: VTX-801
	Version: 9 dated 07 AUG 2023
	Author: Aixial Group CRO

Adverse events	Section 9.2
Concomitant medications	Section 8.1.2

10.5.10 Visits 33-35 (Weeks 15, 16 and 20 ± 3 days)

Refer to Table 3 Summary of Schedule of Events: Weeks 13 to 52 (End of Year 1)				
Visits 33-35	Weeks 15, 16, 20 ±3 days	Follow-up	Home nurse visits	Cross-reference
Vital signs				Section 8.1.4
Local Laboratory: Liver biochemistry panel				Section 8.1.12
Adverse events				Section 9.2
Concomitant medications				Section 8.1.2
Additional for Visit 35, Week 20 only:				
Ceruloplasmin (enzymatic assay and nephelometry), total Cu, REC, RAC, CuEXC, ANCC and CRP				Section 8.1.13
24-hour urinary copper				Section 8.1.13
Visit 35, Week 20: A call or a video consultation between Investigator and patient (check for patient health and for the occurrence of any adverse event since the last visit)				

10.5.11 Visit 36 (Week 24 ± 3 days)

Refer to Table 3 Summary of Schedule of Events: Weeks 13 to 52 (End of Year 1)				
Visit 36	Week 24 ± 3 days	Follow-up	Outpatient visit	Cross-reference
Vital signs				Section 8.1.4

Protocol VTX-801_CLN_001	Investigational Product: VTX-801
	Version: 9 dated 07 AUG 2023
	Author: Aixial Group CRO

Physical examination	Section 8.1.3
Alcohol consumption	Section 7.7
Central Laboratory: Blood/urine biochemistry; hematology; Coagulation	Section 8.1.11
Central Laboratory: Liver biochemistry panel	Section 8.1.11
Local Laboratory: Liver biochemistry panel	Section 8.1.12
Ceruloplasmin (enzymatic assay and nephelometry), total Cu, REC, RAC, Exchangeable Cu, ANCC	Section 8.1.13
24-hour urinary copper For patients on copper chelator: 
Patients have to be reminded to have a 72-hour period without copper-chelator treatment:
48 hours prior starting sampling of urine,And during the 24 hours of urine collection.They will restart their copper-chelator treatment only after the last sampling of the 24-hour urine collection.	Section 8.1.13
Vector shedding: blood, urine, saliva, feces - mandatory Note: at all visits until end of year 1, as applicable, vector shedding sampling is to occur at every site scheduled visit until 3 consecutive concerned samples are negative (at or below quantification limit)	Section 8.2.3
Calculation of MELD, APRI, FIB4 by CRO	Section 8.1.14 Table 11
Ophthalmology: slit lamp examination	Section 8.1.6
Adverse events	Section 9.2
Concomitant medications	Section 8.1.2

Protocol VTX-801_CLN_001	Investigational Product: VTX-801
	Version: 9 dated 07 AUG 2023
	Author: Aixial Group CRO

